Hospital, both located in Baltimore, MD. For the purposes of this study, Sinai Hospital will serve as the community/catchment area. Nurse home visitors recruit these new mothers while they are still in the hospital/maternity ward. Following Dodge et al. (2013; 2014), when the [REDACTED] officially begins, nurse home visitors will enroll new mothers into MFC every other day only (on odd dates). Those new mothers who are not City residents and/or give birth on an even date will not be offered MFC. They will be considered the "control" group and are expected to access community services as they normally would. [REDACTED] staff will recruit ALL Baltimore City residents who give birth at Sinai Hospital, regardless of odd/even birth date, while they are still in the hospital/maternity ward and with post-discharge outreach. If a mother who gives birth on an odd date declines the MFC program, she will still be recruited into the research study. Given that the effects of MFC are a key study question, and MFC is being provided on a random-assignment basis according to child birthdate, this study follows a RCT design. At the same time, we note that its approach is different than many RCT's, in that prospective research participants are not being explicitly invited to be randomized.

3 \* **Describe the relevant prior experience and gaps in current knowledge. Describe any relevant preliminary data:**  
 While nurse home visiting programs have been shown to be effective in reducing infant injuries and improving outcomes for children and families, Family Connects is the first nurse home visiting program to be implemented on a community-wide scale. Evaluations of the Family Connects Program has been conducted by Dodge and colleagues in Durham, North Carolina (Dodge et al., 2013; 2014), demonstrating positive effects such as reduced infant emergency room use and overnight hospital stays, increased families' use of community resources, and improved family well-being. No randomized controlled trials of Family Connects have occurred outside of North Carolina, however. The proposed study seeks to expand the research on the Family Connects Program and assess its outcomes in a mid-sized, mid-Atlantic city.

4 \* **Provide the scientific or scholarly background, rationale, and significance of the research and how it will add to existing knowledge:**  

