## Supporting Literature

1 \* **Provide a summary of current literature related to the research: *If you uploaded a separate research protocol document in the 'Research Protocol' page, cite the applicable section and page numbers from that document in the answer box below.***

Family Connects is a universal nurse home visiting program designed by Dodge and colleagues at Duke University (Dodge et al., 2013; 2014). Family Connects is the first program of its kind to be implemented on a community-wide scale. Family Connects was developed as a brief, universal, postnatal nurse home visiting intervention intended to screen for risk, provide brief intervention, and connect families with more intensive evidence-based services as needed. Family Connects is not intended to be a substitute for intensive programs or services, but is meant to serve as a universal screening to ensure that families are matched with services within their own communities that most appropriately meet the identified needs. A primary goal of Family Connects is to reduce the incidence of infant injury and use of emergency medical care in the first year of life.

Family Connects is available to every family in the designated catchment area. Once screening has occurred, however, families with higher needs are triaged and referred to appropriate services.

Family Connects is highly structured and consists of 3 to 7 scripted in-person or telephone contacts, with the first contact is at the hospital immediately following the infant's birth followed by 1 to 3 nurse home visits when the child is 3 to 8 weeks old, 1 or 2 nurse contacts with community service providers and/or maternal and infant health care providers, and an in-person or telephone follow-up conversation 1 month later.

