## Study Procedures

**If you uploaded a separate research protocol document in the 'Research Protocol' page, cite the applicable section and page numbers from that document in the answer boxes below. (If this study is a collaborative UM/VA study please list each procedure that is being conducted and the locations where it is being conducted.)**

1 \* Describe all procedures being performed for research purposes only (these procedures would not be done if individuals were not in the study) and when they are performed, including procedures being performed to monitor subjects for safety or to minimize risks:

Research staff will visit the Sinai Hospital maternity ward on a daily basis. They will receive regular updates from maternity and MFC staff about new births to Baltimore City residents. For approximately one year and a half starting July 15, 2019, all Baltimore City residents who give birth on an odd date at Sinai Hospital will be offered MFC by nurse home visitors employed by [REDACTED]. From July 15, 2019 – January 14, 2021, research staff will approach ALL new mothers (Baltimore City residents giving birth on even or odd dates) within 1-3 days of the birth of the baby, while they are still in the hospital/maternity ward. The researchers will provide mothers with a brief description of the study and a 1-page information sheet (attached). The researchers will request permission to contact the mothers when their infants are approximately 6 months old to schedule the in-home psychosocial interview. During the hospital meeting, the researchers will confirm mothers' contact information and share their own contact information.

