For those mothers who were unable to complete the recruitment process (e.g. because of interruptions by medical staff or visitors, patient falling asleep), our study team will use the phone number provided by Sinai Hospital to call the mother. Similar to in-person recruitment, during the phone call it will be explained that we are conducting a study about what it's like to raise a baby in Baltimore City with mothers who gave birth at Sinai Hospital and are city residents. We will explain that the study is being conducted in partnership with Sinai Hospital, read through the 1-pager, confirm contact information, and ask her permission to be contacted for a psychosocial interview when her baby is about 6 months old. For those mothers who are discharged before starting the recruitment process, our study team will send a letter and the project's 1-pager to the address provided by Sinai Hospital that introduces the study and states that we will be calling. We will then call using the aforementioned protocol.

All mothers who agree to be contacted will also receive 5 monthly postcards providing a "fun fact" about typical infant developmental milestones. In addition, a member of the research team will send mothers one text message per month from the RA's work cell phone. These text messages will remind them that we will be inviting them to participate in the psychosocial interview around the time of their infant's 6-month birthday. These postcards and text messages will serve the secondary purpose of our staying in touch with the prospective participants and becoming aware, in real time, of any changes in address or phone numbers. Research staff will copy/paste the monthly text message from the Notes app or manually type in each message. If a mother texts the RA's work cell phone with questions about the study, the RA will respond with the appropriate information (e.g., interview location). In cases where a mother may disclose concerning information (e.g., depressive symptoms), information about mental health resources will be provided. This list will include resources from [REDACTED] and other appropriate community referrals.

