## Sample Size and Data Analysis

**If you uploaded a separate research protocol document in the 'Research Protocol' page, cite the applicable section and page numbers from that document in the answer boxes below.**

1 \* Provide the rationale and sample size calculations for the proposed target population:  
Following guidelines established by Cohen (1988) and using Gpower software (Faul et al., 2009), power analyses estimating at least 0.80 power and a significance level of 0.05 indicated that a sample size of 400 (assuming equal groups) will detect small to medium effects in most of the outcomes of interest. Some outcomes are more exploratory in nature. In addition, it is possible that additional research funding garnered in the course of this study will allow for an increased sample size.

2 \* Provide the plan for data analysis. Include in the description the types of comparisons that are planned (e.g., comparison of means, comparison of proportions, regressions, analysis of variance, etc.), which is the primary comparison/analysis, and how the analyses proposed will relate to the primary purposes of the study:  
The principal independent variable will be MFC group (MFC participant/non-participant). The dependent variables of interest will be (a) infant emergency room use and overnight hospital stays; (b) family use of community resources and child care; (c) maternal wellbeing; and (d) quality of the home environment. We will also explore long-term differences between MFC and non-MFC participants in (a) rates of official investigations for child maltreatment and (b) two indicators of early educational achievement: kindergarten readiness scores and rates of kindergarten attendance.

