## Informed Consent Process

**If the study does not involve interaction with participants or a waiver of consent is being requested , answer "N/A" to the questions below.**

1 \* Indicate the type(s) of consent that will be involved in this study: (check all that apply)

- Not applicable (study may qualify as exempt)
- Request to Waive Consent/Parental Permission (Consent is not being obtained)
- Request to Alter Consent (Some Elements of Consent Waived)
- Request to Waive Documentation of Consent (Verbal/Oral Consent)
- Written Consent Form
- Electronic Consent

2 \* Describe the Informed Consent process in detail:

From July 15, 2019 - January 14, 2021, research staff will approach all of these new mothers within 1-3 days of the birth of the baby. The researchers will provide mothers with a brief description of the study and a 1-page information sheet (see attached). The study will be explained to the mothers as a "study of what it is like to raise a baby in Baltimore City." The researchers will request verbal permission to contact the mothers when their infants are approximately 6 months old to schedule the in-home or virtual interview assessment. Informed consent will be collected at the time of this assessment. For virtual interviews, the consent form will be read to participants word-for-word and participants will consent verbally. During the initial contact, the researchers will also confirm mothers' contact information and share their own contact information. Last, all mothers who agree to be contacted will also receive monthly postcards providing a "fun fact" about typical infant developmental milestones.

3 Confirm that the consent process will explain the following:

- The activities involve research.
- The procedures to be performed.
- That participation is voluntary.
- The name and contact information for the investigator.

\*  Yes  No

4 \* Describe who will obtain Informed Consent:

Research staff from the University of Maryland will obtain the Informed Consent document (or verbal consent) from participants.

5 \* If obtaining consent from a legally authorized representative (LAR), describe how you will confirm that the individual is the LAR and can provide legally effective informed consent. (Answer "N/A" if not obtaining consent from LARs)

N/A

6 \* Describe the setting for consent:

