Effects of Early Community Services on Child and Family Development

ClinicalTrials.gov Identifier: NCT04019977

Last updated: July 18, 2023

Statistical Analysis Plan

The principal independent variable will be MFC group (MFC participant/non-participant). The dependent variables of interest will be (a) infant emergency room use and overnight hospital stays; (b) family use of community resources and child care; (c) maternal wellbeing; and (d) quality of the home environment. We will also explore long-term differences between MFC and non-MFC participants in (a) rates of official investigations for child maltreatment and (b) two indicators of early educational achievement: kindergarten readiness scores and rates of kindergarten attendance.

A two-tailed intent-to-treat design analysis will include all randomly assigned families (regardless of actual intervention participation). Ordinary least squares regression models will be used to estimate impact of MFC on continuous and categorical outcomes. Poisson regression models will be used for count variables with skewed distribution. Covariates for all models will include the following: Medicaid status (yes/no) at birth and at 6 months, mother race/ethnicity (nonminority/minority), single parent household (yes/no), birth complications (yes/no) including maternal health conditions affecting the baby, infant injuries from birth trauma, and infant distress. Exploratory moderators will include infant birthweight, family Medicaid status, and mothers' adverse childhood experiences and adult attachment security. All results will be analyzed at the .05 significance level.

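### The plan promises an intent-to-treat analysis of all randomly assigned families, but only families who agree to contact and consent at about 6 months can be analysed

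*SAP*

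**What the plan says.** Both documents give one sentence on who is analysed (SAP, second paragraph; Protocol, Sample Size and Data Analysis, item 2): "A two-tailed intent-to-treat design analysis will include all randomly assigned families (regardless of actual intervention participation". The preceding paragraph names the comparison: "The principal independent variable will be MFC group (MFC participant/non-participant".

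On assignment, Protocol, Justification, Objective, & Research Design, item 2, says "MFC is being provided on a random-assignment basis according to child birthdate". Odd dates are offered MFC and even dates are not. Odd-date mothers who decline MFC are still recruited to the research.

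Research contact comes after birth. In Study Procedures, item 1, "The researchers will request permission to contact the mothers when their infants are approximately 6 months old to schedule the in-home psychosocial interview". Under Informed Consent Process, item 2, the approach window runs from July 15, 2019 to "January 14, 2021, research staff will approach all of these new mothers within 1-3 days of the birth of the baby". Mothers who leave hospital earlier are followed up: "For those mothers who are discharged before starting the recruitment process, our study team will send a letter", and a call comes next, with no time limit given. Informed consent itself is taken at the 6-month assessment (Recruitment, item 1; Informed Consent Process, item 2). The programme description places "1 to 3 nurse home visits when the child is 3 to 8 weeks old" (Supporting Literature, item 1), well before consent.

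**The concern.** An intent-to-treat claim takes its strength from keeping everyone who was assigned. Here assignment happens at birth, and two later decisions by the mother determine whether the study has any outcome for her family. The second comes after the MFC visits, so the intervention could in principle affect who is reachable or willing. Balance from the odd/even rule is then not guaranteed among those analysed.

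If the sentence stands, a comparison of consenting families can be presented as covering all assigned families. Neither document plans counts by assigned group, so a reader would have no means of judging the difference.

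The group variable adds to this. Taken literally, participant versus non-participant puts odd-date mothers who declined MFC with the controls, which the intent-to-treat sentence rules out.

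**Working it through.** **1. Can the stated set be formed?** The steps in order:

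| Step | Timing | Source (Protocol) |
|---|---|---|
| Assignment by birth date | birth | Justification, Objective, & Research Design, item 2 |
| Permission to be contacted | 1 to 3 days after birth, or later by phone or letter | Study Procedures, item 1; Recruitment, item 1 |
| MFC home visits | 3 to 8 weeks | Supporting Literature, item 1 |
| Scheduling call, to mothers who agreed | about 6 months | Study Procedures, item 1 |
| Informed consent, then interview | about 6 months | Recruitment, item 1; Informed Consent Process, item 2 |
| Record access and matching, for those who consented | after consent | Study Procedures, item 1 |

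Interview outcomes need both permissions. Hospital, human-services, MFC and education records need permission on the same consent form, so they do not fill the gap. I found no waiver of consent in the text; the waiver section concerns written documentation only. An assigned family lost at either step has no outcome available to the study. The parenthesis in the analysis sentence covers families who do not take up MFC, not families who are never reached or do not consent.

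Among consenters, some data may still be missing: mothers may decline questions (Privacy of Participants, item 1), and record access may end on withdrawal (Withdrawal of Participants, item 2).

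**2. The plan's own figure.** N = 400, equal groups, power at least 0.80, significance level 0.05, small to medium effects (Sample Size and Data Analysis, item 1). No numeric effect is given, so 400 cannot be reproduced strictly. Solved backwards with 200 per group: SE = sqrt(2/200) = 0.10 SD, and the detectable difference is 2.80 × 0.10 = 0.28 SD. That fits the description. Enrolled means consented (Participant Selection, item 2), so the power statement already rests on consenters and renaming the set does not change it.

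**3. What 700 and 400 show.** 400/700 = 57.1% of those screened; the other 300 are 42.9%. This is not a loss rate among assigned families. Screening includes eligibility checks, non-English speakers are excluded, and the number assigned is not stated.

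**4. Illustration only.** Assumptions not in the documents: all 700 are assigned families; losses before agreement to contact are the same in both groups; a share f of the 300 losses comes after agreement; consent rates are equal; and the outcome gap between consenters and non-consenters differs between groups by g. Then A = 400 + 300f, m = 1 − 400/A, bias = m × g, and type I error = P(|Z + bias/0.10| > 1.96).

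| f | A | m | Bias, g = 0.1 SD | Error | Bias, g = 0.2 SD | Error |
|---|---|---|---|---|---|---|
| 0 | 400 | 0 | 0 | 5.0% | 0 | 5.0% |
| 0.25 | 475 | 0.158 | 0.016 | 5.3% | 0.032 | 6.2% |
| 0.5 | 550 | 0.273 | 0.027 | 5.9% | 0.055 | 8.5% |
| 0.75 | 625 | 0.360 | 0.036 | 6.5% | 0.072 | 11.1% |
| 1 | 700 | 0.429 | 0.043 | 7.1% | 0.086 | 13.7% |

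With g = 0 the bias is 0 and the error 5% throughout. The g = 0.1 columns also stand for covariates absorbing half of a 0.2 SD gap.

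**5. A calendar check.** July 15, 2019 to January 14, 2021 is 550 days, 281 odd and 269 even. If births and recruitment were even over the whole planned window and selection equal, 400 × 281/550 = 204 consenters would have odd dates (95% range 185 to 224). At an assumed mean consent rate of 57%, the chance of flagging a difference of 10, 15 or 20 points is 0.40, 0.73 or 0.93.

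**The case against.** The strongest reply is that the sentence exists to keep MFC decliners in their group. The protocol describes an earlier Family Connects trial as intent-to-treat although 549 families were analysed out of 4777 assigned, and this study follows that trial. Enrolment and power are both openly set at 400, so the defect is one loose phrase. Much of this stands: analysing a subset by assignment is legitimate. But the protocol calls that earlier set a subset, whereas this plan names none. The SAP was last updated in July 2023, after the planned recruitment window had closed.

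A reader might infer that 43% of assigned families are lost, that the trial's error rate is near 14%, or that MFC contact changes who consents. The documents support none of these. The 43% is a share of screened mothers. The 14% needs every one of the 300 to be an assigned family lost after agreeing to contact, plus an assumed 0.2 SD differential gap. No passage shows differing selection, and the protocol guards against it: the study is introduced neutrally, research staff do not discuss MFC, and all who agree to contact get the same postcards and texts. One point stays open. Of the research staff, the protocol says "They will receive regular updates from maternity and MFC staff about new births to Baltimore City residents", and MFC staff enrol on odd dates only. The hospital also supplies patient information, which limits the worry.

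It can also be said that the group variable is a separate conflict. It does not depend on consent, but it bears on the same question of who is compared with whom, and is best settled in the same edit.

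**Conclusion.** The sentence is wrong as written: it gives the analysis a property that the consent procedure rules out. This rests on the documents' text alone and holds even if selection bias is nil. The attainable analysis is of consenting families by birth-date group, open to selection after assignment. Whether that selection differs by group, and by how much, cannot be derived from the documents; the bias and error figures are illustration only. The calendar check is weak: it finds only large differences, its benchmark assumes even births and recruitment over the full planned window, and a balanced share would not prove equal selection. The point should be corrected because it alters what the trial can claim, at little cost. It is not evidence that the results are biased.

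**What to change.** 1. In the SAP and in Protocol, Sample Size and Data Analysis, item 2, replace the analysis-set sentence with: *The analysis includes all families who consented at about 6 months, analysed by assigned group (odd or even birth date) regardless of MFC participation.* Do not call this set all randomly assigned families. The wording deliberately sets no complete-case rule; handling of missing outcomes and covariates among consenters remains a separate choice.
2. In the same two places, define the principal independent variable as assigned group (odd or even birth date), so that mothers who decline MFC stay in their assigned group.
3. Report the numbers who agreed to contact, consented and were analysed (per outcome) by birth-date parity, as far as records allow, and state selection after assignment as a limitation. Any comparison of the odd-date share of consenters with the calendar share should use the actual recruitment dates and be described as a weak check.

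Items 1 and 2 are wording. Item 3 is a tabulation; the documents do not say whether birth dates are held for mothers who never agreed to contact. The calendar comparison needs only consenters' birth dates and the actual recruitment dates. No new data collection and no change to consent timing is asked for.

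### Ordinary least squares is the only model for categorical outcomes and robust errors are not mentioned, so exploratory moderator tests on yes/no outcomes can miss their 5% level

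*SAP*

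**What the plan says.** The second paragraph of the SAP sets the models: "Ordinary least squares regression models will be used to estimate impact of MFC on continuous and categorical outcomes". The protocol has the same sentence under Sample Size and Data Analysis, item 2, so it is not a copying slip. The only other model is for counts: "Poisson regression models will be used for count variables with skewed distribution". Neither document mentions a logistic, ordinal or multinomial model, a robust variance, or a rule for coding categories.

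Neither document lists which outcomes are categorical. Two exploratory long-term outcomes are given as rates: "rates of official investigations for child maltreatment" and, within "two indicators of early educational achievement: kindergarten readiness scores and rates of kindergarten attendance", attendance. One main outcome domain is "family use of community resources and child care", with no coding given.

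On moderators the SAP says: "Exploratory moderators will include infant birthweight, family Medicaid status, and mothers' adverse childhood experiences and adult attachment security". On the error level it says: "All results will be analyzed at the .05 significance level".

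**The concern.** Classical least squares assumes one residual variance for everybody. A yes/no outcome with event probability p has variance p(1-p), so the variance changes wherever the risk changes. A moderator test compares the arm difference between groups. If those groups differ in size and in risk, the pooled variance is wrong for that comparison and the test no longer runs at 5%. It becomes too liberal when the smaller group has the larger variance, and too conservative when the larger group does.

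A second issue would arise for an outcome with three or more unordered levels. Its least-squares coefficient depends on the numbers given to the levels.

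At stake is the reading of who benefits from the programme. A moderator result declared at .05 could be a false positive several times more often than stated, or a real difference could be missed because the test is too strict.

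**Working it through.** **Stated figures.** The protocol gives 400 families in equal groups, power of at least 0.80 and a .05 level. It gives no numeric effect size, outcome rate or moderator split, and no error rate for any test. The 400 can only be back-solved: (1.960 + 0.842) × √(2/200) = 0.280, so 200 per arm gives 80% power at a standardised difference of 0.28. Nothing below depends on that.

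**Set-up.** N = 400, equal arms, no true arm effect or interaction, two-sided 5%. A share q of families is in the moderator group with risk p1; the rest have risk p0. All q, p1 and p0 are assumptions.

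- Per-arm sizes: n1 = 200q, n0 = 200(1-q). Variances: v1 = p1(1-p1), v0 = p0(1-p0).
- True variance of the interaction estimate: V = 2v1/n1 + 2v0/n0.
- Variance that least squares reports: V_OLS = [q·v1 + (1-q)·v0] × (2/n1 + 2/n0).
- With r = √(V_OLS/V), the actual error rate is 2[1 - Φ(1.96r)].

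**Small group at higher risk** (q = 0.10, 10% v 2%): n1 = 20, n0 = 180, v1 = 0.0900, v0 = 0.0196.
- V = 0.00900 + 0.00022 = 0.00922.
- V_OLS = 0.02664 × 0.1111 = 0.00296.
- r = 0.567; error rate 26.7%.

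**Large group at higher risk** (q = 0.80, 10% v 2%): n1 = 160, n0 = 40.
- V = 0.001125 + 0.000980 = 0.002105.
- V_OLS = 0.07592 × 0.0625 = 0.004745.
- r = 1.501; error rate 0.3%.

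**Range by the same formula:**

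| Share in group | Risk in group v others | Error rate |
|---|---|---|
| 10% | 10% v 10% | 5.0% |
| 10% | 10% v 2% | 26.7% |
| 10% | 20% v 5% | 21.8% |
| 10% | 30% v 10% | 16.0% |
| 10% | 30% v 2% (extreme) | 37.8% |
| 20% | 10% v 2% | 19.2% |
| 20% | 20% v 5% | 16.2% |
| 20% | 30% v 10% | 12.5% |
| 20% | 20% v 10% | 9.8% |
| 60% | 10% v 5% | 3.7% |
| 80% | 10% v 5% | 1.8% |
| 80% | 10% v 2% | 0.3% |

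At a 50/50 split the rate is 5.0% whatever the risks.

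**Simulation.** Models with arm, moderator and interaction (8,000 runs per setting) agree. Six of the small-group settings above (all except the equal-risk, extreme and 20% v 10% rows) give 12.7% to 26.7%. The large-group settings (60-80% of families, 10% v 2-5%) give 0.4% to 4.0%. With HC3 errors both sets fall at about 4% to 5%. The plain arm test under classical least squares stays at 4.7% to 5.3% in 10,000-run simulations with equal arms. With birthweight kept continuous, the classical interaction test rejects about 6% to 9% of the time. None of these runs includes the SAP's covariates, and the childhood-adversity and attachment moderators were not simulated.

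**Unordered levels, if any exist.** Take an assumed three-level outcome, 40/30/30% in one arm and 30/50/20% in the other, 200 per arm.
- Codes 1, 2, 3: means 1.9 and 1.9, difference 0, power 5%.
- Codes 1, 3, 2: means 1.9 and 2.2, difference +0.3, power 94%.
- Codes 2, 1, 3: means 2.0 and 1.7, difference -0.3, power 97%.

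A 2-df chi-square test, which uses no codes, has 97%.

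**Logistic interaction tests when events are sparse.** With 80% of families in a group at 10% risk and 2% in the others, each arm has 40 of the others. The chance of no event in one such cell is 0.98^40 = 0.446, so at least one of the two is empty in 1 - (1 - 0.446)² = 69% of data sets, and the logistic interaction then has no finite estimate. The Wald test rejects about 0.0% of the time there. In a milder case (80% of families, 30% v 10%) it rejects 2.3%, against 5.1% for least squares with HC2 robust errors.

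**The case against.** A linear probability model is a legitimate analysis of a yes/no outcome, and what is missing is one phrase about standard errors. Silence on robust errors is also not a decision against them. This stands in part: least squares as such is not the defect, but an analyst who follows the text as written would use classical errors.

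Three stronger readings are tempting, and the documents do not support them.

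- **That the main yes/no comparisons are invalid.** They are not; with equal arms the plain arm test keeps its level.
- **That unordered outcomes are being tested on arbitrary codes.** No unordered outcome is named. Child care type would be one, but the SAP speaks of use, and the protocol's hypothesis (Justification, Objective, & Research Design, item 1) of higher quality.
- **That the birthweight test will be wrong by a factor of three to five.** The SAP lists birthweight itself, with no low-birthweight category or cut-off. Kept continuous, it gives about 6% to 9%.

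It is also fair that maltreatment investigations could be analysed as counts, for which the SAP has Poisson regression, and that attendance could be a proportion of days. The yes/no problem applies only to outcomes analysed as any/none. Finally, the moderators are labelled exploratory. That lowers the weight of the point, but the SAP holds every result to .05, so the level should be true.

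**Conclusion.** The point holds in limited form and is minor. The rule for categorical outcomes is stated in both documents, and nothing in them corrects the standard errors. Exploratory moderator tests on yes/no outcomes can therefore run at about 10% to 27% for a higher-risk minority of 10-20% of families, or at about 0.4% to 4% for a higher-risk majority of 60-80%. The error goes one way for any given moderator and outcome. It disappears with equal group sizes or equal risks, and reaches about 38% only in an extreme case.

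These sizes rest on assumed splits and rates, 400 families, equal arms, classical errors and no covariates. The mechanism does not depend on the particular values; the size does. The meaninglessness of least squares on unordered codes is certain in principle, but conditional here on such an outcome existing.

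**What to change.** List the type of each outcome (continuous, count, yes/no, ordered, unordered) and replace the model sentence with wording to this effect:

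- Continuous outcomes: ordinary least squares.
- Yes/no outcomes: linear probability model with HC3 robust standard errors, for the arm effect (a risk difference) and for moderator tests; logistic regression as a sensitivity analysis where cells are not sparse.
- Ordered categories: proportional-odds regression.
- Any unordered outcome: multinomial logistic regression with one overall test of assignment.

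The linear model with HC3 errors should lead for moderator tests because logistic Wald tests can be far too conservative, or have no finite estimate, when events are few. The choice also fixes the scale on which moderation is judged, the risk difference. The Poisson rule for skewed counts can stay. The cost is SAP wording and slightly more analysis work; no new data are needed.
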